4.2 Handling and Dispensing

The investigational product should be stored in a secure area according to local regulations. It is the responsibility of the Investigator to ensure that investigational product is only dispensed to Patients. The investigational product must be dispensed only from official study sites by authorized personnel according to local regulations.

The applicable site personnel should ensure that the study drugs are stored in accordance with the environmental conditions (temperature, light, and humidity) determined by the Sponsor. If concerns regarding the quality or appearance of the study drugs arise, do not dispense the study drugs and contact the Sponsor or designee immediately.

Study drug documentation including all processes required to ensure drug is accurately administered must be maintained. This includes documentation of drug storage and administration and, as applicable, storage temperatures, reconstitution, and use of required processes (e.g. required diluents, administration sets).

Please refer to the current version of the Investigator Brochures and/or pharmacy manual for complete preparation, storage, and handling information.

4.2.1 Cabiralizumab

The investigational supply of cabiralizumab will be provided to the study centers by Bristol-Myers Squibb and will be administered to patients in the clinical study by a trained healthcare professional.

Cabiralizumab drug product is supplied for IV administration as a sterile, aqueous, colorless to pale yellow liquid, clear to slightly opalescent pyrogen-free solution in 7 mL glass vials stoppered with coated stoppers, and equipped with aluminum seals. Light (few) particulates (consistent in appearance to proteinaceous particles) may be present. Each vial contains a minimum of 7 mL of a 20 mg/mL solution of cabiralizumab (approximately 140 mg per vial). Storage Conditions: 2–8°C (36–46°F). The vials will be provided in a carton. Both vials and cartons will be labeled per local regulations.

Refer to Cabiralizumab Investigator's Brochure for more specific information on the drug product.

4.2.2 Nivolumab

The investigational supply of nivolumab will be provided to the study centers by the Bristol-Myers Squibb.

Nivolumab Injection, 100 mg/10 mL (10 mg/mL) is a clear to opalescent, colorless to pale yellow liquid, which may contain light (few) particulates. The drug product is a sterile, non-pyrogenic, single-use, isotonic aqueous solution formulated at 10 mg/mL in sodium citrate, sodium chloride, mannitol, diethylenetriaminepentacetic acid (pentetic acid), and polysorbate 80 (Tween 80), pH 6.0 and includes an overfill to account for vial, needle, and syringe holdup. It is supplied in 10-cc Type I flint glass vials, stoppered with butyl rubber stoppers and sealed with aluminum seals.

Nivolumab injection is to be administered as an IV infusion through a 0.2-micron to 1.2-micron pore size, low-protein binding (polyethersulfone membrane) in-line filter at the protocol specified doses and infusion times. It is not to be administered as an IV push or bolus injection. Nivolumab injection can be infused undiluted (10 mg/mL) or diluted with 0.9% Sodium Chloride Injection, USP or 5% Dextrose Injection, USP to protein concentrations as low as 0.35 mg/mL.

During drug product preparation and handling, vigorous mixing or shaking is to be avoided.

Care must be taken to assure sterility of the prepared solution as the product does not contain any antimicrobial preservative or bacteriostatic agent. Nivolumab infusions are compatible with polyvinyl chloride (PVC) or polyolefin containers and infusion sets, and glass bottles.

Vials of nivolumab injection must be stored at 2 degrees C to 8 degrees C (36°F to 46°F) and protected from light and freezing. The administration of nivolumab infusion must be completed within 24 hours of preparation. If not used immediately, the infusion solution may be stored under refrigeration conditions (2°C to 8°C, 36°F to 46°F) for up to 24 hours, and a maximum of 8 hours of the total 24 hours can be at room temperature (20°C to 25°C, 68°F to 77°F) and room light. The maximum 8-hour period under room temperature and room light conditions includes the product administration period.

Refer to the Nivolumab Investigator's Brochure for more specific information on the drug product.

4.2.3 APX005M

The investigational supply of APX005M will be provided to the study centers by Apexigen.

APX005M is supplied in 20 mL Type 1 clear glass vials for IV administration. Each vial contains 10 mg APX005M/mL in a sterile, clear to slightly opalescent, colorless to slightly yellow, preservative-free solution (pH 5.5) containing 25 mM sodium acetate, 248 mM trehalose, and 0.02% polysorbate 20 in water for injection (WFI). The 20 mL vials are intended for single use.

APX005M is intended for IV infusion. For use, APX005M is diluted in normal saline and infused via IV infusion or syringe pump.

Refer to the APX005M Investigator's Brochure for more specific information on the drug product.

4.3 Method of Assigning Patient Identification

Patients must be able to provide written informed consent and meet all eligibility criteria. No waivers of inclusion or exclusion criteria will be granted by Sponsor or its designee for any patient enrolled in the study. Before enrolling a patient, all eligibility criteria must be satisfied.

See Section 4.4.1 and Figure 6 for dosing schema. Patients who qualify for Phase 1 dose escalation of the study will be enrolled as follows:

- Cohort 1 will be enrolled first and these patients will be followed one 14-day cycle.
- Once the DLT follow-up period of 28 days is cleared for Cohort 1, simultaneous enrollment to Cohort 2 and Cohort 3 will occur. Patients in these cohorts will be treated for a total of one 14-day cycle.
- Simultaneous enrollment into Cohort 4 and Cohort 5 will proceed once the 14-day DLT

period for dose escalation is cleared in the preceeding Cohorts 2 and 3.

- Once the DLT period of 28 days for dose escalation is cleared Cohorts 4 and 5, enrollment to the final Cohort 6 will occur.
- The MTD will be calculated for patients who have received at least 2 cycles (at least 28 days) of study drug.
- Dose escalation into sequential dose levels of APX005M in combination with cabiralizumab and nivolumab may proceed until DLTs are observed either in the cabiralizumab/APX005M doublet therapy cohorts 1, 3, and 5 or in the nivolumab/cabiralizumab/APX005M triplet therapy cohorts after discussion and agreement between the PIs and Industry Collaborators.

In Phase 1b, a maximum of 34 patients will be enrolled per disease-specific cohort (advanced melanoma, NSCLC, or RCC). Enrollment will be open for all cohorts in parallel and will continue until the enrollment target is reached. Once a disease cohort is filled, further enrollment will be restricted to the cohort(s) that have not been filled. A total of approximately 102 patients will be enrolled in the Phase 1b arm of the study.

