If none of the first 3 evaluable patients in a dose cohort experience a dose-limiting toxicity (DLT) in the first two cycles, then the next 3 patients will be treated at the next higher dose cohort. If 1 of 3 patients within a cohort experiences a DLT in the first two cycles, then 3 additional patients will be added to that cohort. If a second patient experiences a DLT at that dose level in the first two cycles, the next cohort will not be initiated, and the dose of one or more drugs will be de-escalated. Patients at each dose level will be evaluated for at least 4 weeks from the start of treatment before additional patients can be treated at a higher dose level. If DLTs are observed in 2 or more patients within a cohort, the maximum tolerated dose (MTD) will have been exceeded and no further patients will be treated at that dose level. At 8 weeks, imaging studies will be performed to assess for response. Of note, 2 sets of cohorts will be conducted simultaneously: Cohorts 2 and 3, and Cohorts 4 and 5, as depicted below.

Dose escalation will be based on the number of DLTs experienced during the DLT evaluation interval as determined by dose escalation meetings attended by the PIs and Industry Collaborators (see Section 3.1.2.1.1 for DLT criteria). The DLT evaluation interval begins on the first day of treatment and continues for 28 days.

Algorithm for Dose-Escalation Decisions

Number of Patients with DLT at a Given Dose Level	Dose Escalation Decision Rule
0/3	Escalation will occur into the next highest dose cohort
1/3	Enroll 3 additional patients at current dose level
≥2/3	Stop enrolment. Enroll 3 more patients at the lower dose level, if only 3 were previously entered, or at an intermediate dose level.
1/6	Open next cohort
≥2/6	Stop enrolment. Enter 3 more patients at the lower dose level or at an intermediate dose level.

Phase 1b Study

Once a specific dose regimen is determined to be safe as determined by the Sponsors and Industry Collaborators, the phase 1b portion will follow and will enroll additional patients in three disease-specific cohorts, all of whom who have progressed on prior PD-1/PD-L1 therapy: advanced melanoma, NSCLC,

and RCC who have progressed on prior PD-1/PD-L1 therapy. Patients will be treated at the estimated APX005M RP2D in combination with nivolumab 240 mg IV and cabirizumab 4 mg/kg on day 1 of each 14-day cycle.

Number of Patients

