3.1 Study Design and Duration

This study is a Phase 1/1b, open-label, single institution, dose escalation and dose expansion study to evaluate the efficacy, safety, and tolerability of APX005M in combination with nivolumab and cabiralizumab in patients with advanced melanoma, NSCLC, and RCC.

Nivolumab is a fully human monoclonal antibody directed against PD-1. Cabiralizumab is a humanized monoclonal antibody directed against CSF1R. APX005M is a humanized IgG1 agonistic monoclonal antibody that binds CD40.

Patients will be sequentially enrolled in the phase 1 dose escalation portion in 6 cohorts using a standard 3 + 3 design to determine safety, characterize the adverse events, and establish the MTD of APX005M in combination with cabiralizumab and nivolumab. A minimum of 48 hours observation will be required after each patient is enrolled in cohorts 1-6, before a subsequent patient can be enrolled. Approximately 3 patients will be enrolled into each cohort. Cohorts 1, 3, and 5 will include cabiralizumab at the fixed RP2D of 4 mg/kg and dose escalation of APX005M. Cohorts 2, 4, and 6 will include nivolumab at 240 mg, cabiralizumab at 4 mg/kg, and dose escalation of APX005M.

All study drugs will be given on Day 1 of each 14-day treatment cycle. Pre-medications will be given before nivolumab. Nivolumab will be administered as an IV infusion over 30 minutes first followed by a 30-minute break and then cabiralizumab will be administered as an IV infusion over 30 minutes. After another 30-minute break, APX005M will be administered as an IV infusion over 60 minutes. Patients must remain near the vicinity of a hospital with rapid access to an intensive care unit setting during the initial 48 hour period after treatment for the first two treatment cycles.

Dose escalation will be based on the number of DLTs experienced during the DLT evaluation interval as determined by the PI and Industry Collaborators (see Section 3.1.2.1.1 for DLT criteria). The DLT evaluation interval begins on the first day of treatment and continues for 28 days.

The phase 1b portion will enroll patients in three cohorts (advanced melanoma, NSCLC, and RCC) to study the RP2D of APX005M in combination with nivolumab and cabiralizumab.

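### Section 4.3 opens cohorts 4 and 5 after a 14-day DLT period, although section 3.1.2.1 requires two 14-day cycles for the same step

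*Combined protocol and SAP*

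**What the plan says.** Section 4.3 lists the Phase 1 enrolment order step by step. Its gates are:

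- Cohort 1 to cohorts 2 and 3: "Once the DLT follow-up period of 28 days is cleared for Cohort 1", the next two cohorts open together.
- Cohorts 2 and 3 to cohorts 4 and 5: "Simultaneous enrollment into Cohort 4 and Cohort 5 will proceed once the 14-day DLT" period is cleared in cohorts 2 and 3.
- Cohorts 4 and 5 to cohort 6: "Once the DLT period of 28 days for dose escalation is cleared Cohorts 4 and 5", cohort 6 opens.

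The same list has two more 14-day statements: "Cohort 1 will be enrolled first and these patients will be followed one 14-day cycle", and, for cohorts 2 and 3, "Patients in these cohorts will be treated for a total of one 14-day cycle". It then requires two cycles for the MTD: "The MTD will be calculated for patients who have received at least 2 cycles (at least 28 days) of study drug".

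The rest of the protocol uses 28 days. The synopsis says "Patients at each dose level will be evaluated for at least 4 weeks from the start of treatment" before anyone is treated at a higher level. Section 3.1 says "The DLT evaluation interval begins on the first day of treatment and continues for 28" days. Section 3.1.2.1 names the contested step: cohort 4 waits for two cycles in the last patients of cohorts 2 and 3, and cohort 5 waits for two cycles in the last patient of cohort 3. It also sets a general 28-day observation period, counted from the last patient treated in a cohort. Section 3.1.2.1.1 defines a DLT over the first 28 days.

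**The concern.** Two current sections give different opening dates for the same cohorts, and the more permissive one is the list that staff would use to enrol patients. No reason is given for a shorter window at the middle step.

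All drugs are given on day 1 of a 14-day cycle, so the second dose falls on day 15. A 14-day gate therefore covers one dose and half the DLT window. The protocol treats the second cycle as a risk period: sections 3.1 and 4.4.1 keep patients close to intensive care for 48 hours after dosing in each of the first two cycles. Section 1.2 notes that APX005M and cabiralizumab had not been combined before. Section 1.3.6.3.3 reports two serious events in later cycles of single-agent APX005M, though at 1 mg/kg, above any dose planned here.

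At stake is escalation of APX005M to 0.1 mg/kg in the triplet (cohort 4) and 0.3 mg/kg in the doublet (cohort 5) on incomplete DLT data.

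**Working it through.** **Text check.** The protocol's DLT window is 2 cycles × 14 days = 28 days. The 14-day figure for cohorts 4 and 5 cannot be reproduced from any other section. Of the three gates in 4.3, the first and third are 28 days and only the second is 14. Section 3.1.2.1 sets that second gate at two cycles by name.

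**Timing.** I read the 14 days as counted from the last patient. Sections 3.1 and 3.1.2.1 space patients at least 48 hours apart. When patient 3 reaches day 14, patient 2 is at day 16 or later and patient 1 at day 18 or later. Patients 1 and 2 may have had their second dose, with as little as 1 and 3 days of follow-up after it. Patient 3 has not had it.

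At the fastest accrual the stagger allows, three patients in the next cohort start over 2 × 2 = 4 days. If the stagger runs across cohorts 4 and 5 together, six patients start over 5 × 2 = 10 days. Both are shorter than the 14 days by which the gate is brought forward.

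**Chance of clearing 3+3, per cohort.** The documents give neither the DLT rate nor its timing, so both are assumed. Let p be the 28-day DLT rate, f the share of those DLTs seen by day 14, and q = f × p. A cohort clears with 0/3, or with 1/3 followed by 0/3 (Table 3).

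- Full window: (1−p)³ + 3p(1−p)⁵.
- Only the last patient of each set of three cut at day 14 (lower bound, allowing for the stagger): (1−p)²(1−q)[1 + (2p+q)(1−p)²].
- Every patient in a set cut at day 14 (upper bound): (1−q)³ + 3q(1−p)²(1−q)³.

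In both 14-day formulas, when 1/3 triggers expansion the first three patients reach 28 days while the next three are treated.

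At p = 0.40:

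- Full window: 0.216 + 3 × 0.40 × 0.0778 = 0.309.
- Lower bound, f = 0.5 (q = 0.20): 0.36 × 0.80 × [1 + 1.00 × 0.36] = 0.392. With f = 0.8 (q = 0.32): 0.36 × 0.68 × [1 + 1.12 × 0.36] = 0.344.
- Upper bound, f = 0.5: 0.512 + 3 × 0.20 × 0.36 × 0.512 = 0.623. With f = 0.8: 0.314 + 3 × 0.32 × 0.36 × 0.314 = 0.423.

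In each range below, the first figure is f = 0.8 and the second is f = 0.5.

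| 28-day DLT rate | 28-day gate | Last patient cut | All patients cut |
|---|---|---|---|
| 40% | 30.9% | 34.4–39.2% | 42.3–62.3% |
| 30% | 49.4% | 52.6–57.0% | 59.4–75.0% |
| 20% | 70.9% | 73.0–76.0% | 77.5–86.9% |
| 10% | 90.6% | 91.4–92.5% | 93.0–96.2% |

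With f = 0.9 the bounds narrow to 33–36% against 31% at a 40% rate, and to 72–74% against 71% at a 20% rate.

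**The case against.** The strongest reply is that the controlling text is clear and 4.3 contains a slip. Section 4.3 concerns patient assignment. Section 3.1.2.1 governs escalation, sets two cycles for cohorts 4 and 5 by name, and requires a safety teleconference with documented agreement before each new dose level. Since a DLT is defined over 28 days, there is no 14-day DLT period to clear. This stands as a limit on the practical harm. It does not remove the conflict: nothing says which section prevails, and the teleconference sets no length of observation. Section 3.1.2.1 also lets the investigators adopt a different escalation scheme after data review, but that permission sets no 14-day gate.

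The size of the effect can also be challenged. The early-DLT share has no source in the documents. Section 1.3.6.3.2 reports APX005M levels mostly below quantitation between 24 and 168 hours, and section 4.8 places cytokine release within 48 hours of dosing, so for that drug early onset is plausible. A 40% rate is a deliberately unfavourable case. A DLT on days 15–28 would still count and could halt dosing, so clearing the gate is not final escalation. All of this stands and argues for reading the figures as an illustration. But acute reactions follow each dose, and for the last patient the second dose comes after the gate.

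**Conclusion.** The conflict is real and confined to section 4.3. One of three escalation gates is half the length required elsewhere, and two neighbouring statements about one 14-day cycle also depart from the two-cycle rule. Under the stated timing assumption (50–80% of DLTs by day 14), the chance of clearing is 34–62% rather than 31% at a 40% DLT rate, which is above the 33% limit in the MTD definition. At a 10% rate it is 91–96% rather than 91%. The effect is smaller if more DLTs occur early.

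Three stronger readings are tempting, and the documents do not support them:

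- A reader might infer that the MTD or RP2D rests on 14 days of data. Sections 3.1.2.1 and 4.3 both require at least 28 days for that calculation.
- A reader might infer that cohorts 4 and 5 were in fact opened early. The documents do not say which gate was applied.
- A reader might extend the criticism to the DLT list in 3.1.2.1.1 and infer that items 5 and 10 cancel some of item 4's exceptions. The text equally allows the specific exceptions to prevail, and nothing shows that the strict reading was meant.

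**What to change.** In section 4.3, replace the 14-day DLT period for opening cohorts 4 and 5 with a 28-day DLT period (two 14-day cycles). Delete the two statements about one 14-day cycle (follow-up of cohort 1, treatment of cohorts 2 and 3), or correct each to two 14-day cycles (28 days) of DLT observation. Leave the DLT list unchanged.

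The cost is a wording amendment, with no added patients, visits or procedures. The step to cohorts 4 and 5 takes 28 − 14 = 14 days longer than 4.3 now says, which section 3.1.2.1 already requires. If the step has already been taken, the sponsor should still correct the text and record which gate was used.

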3.2 Study Population

3.2.1 Planned Number of Patients

In the Phase 1 dose escalation portion of the trial, we will enroll at least 3 patients per cohort. There are a total of 6 cohorts. In the Phase 1b portion, a Simon two stage design will be used. At least 13 patients per each disease cohort (advanced melanoma, NSCLC, and RCC) will be enrolled in the first phase and in the second phase, an additional 21 patients per disease cohort, for a maximum of 34 patients per disease cohort, are expected to be enrolled, for a total of 102 subjects.

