7.1 Sample Size Determination

The primary endpoint of safety and MTD of APX005M in combination with cabiralizumab and nivolumab will be determined by a 3+3 dose escalation design as described above. In this first phase, patients will be enrolled regardless of disease (melanoma, NSCLC, and RCC). The maximum tolerated dose (MTD) will be estimated independently of cohort. Upon completion of this determination, we will proceed to three parallel two-stage designs, separately for each of the three disease cohorts using the MTD. Patients exposed to the MTD in the dose escalation phase will be carried over to the appropriate two-stage design.

Simon's two-stage design will be used in the phase 1b portion of the trial which will include 3 separate and parallel disease-specific cohorts (melanoma, NSCLC, and RCC). For each of the three tumor types, an immune therapy regimen which is modestly active in patients whose disease had progressed on PD-1/PD-L1 inhibitors would have a response rate (RR) of 10%. The null hypothesis that the true response rate is 10% will be tested against a one-sided alternative. A regimen worthy of further investigation in any of the three tumor types will have a RR of 25%. In the first stage, 13 patients of each cancer will be accrued. If there are 1 or fewer responses in these 13 patients, that cohort will be stopped. Otherwise, 21 additional patients of the same disease cohort will be accrued for a maximum total of 34 patients per disease cohort. Each of the three null hypotheses will be rejected if 6 or more responses are observed in 34 patients for each cohort. This design yields a type I error rate of 0.1 and a power of 80% when the true response rate is 25% in each of the three cohorts. There will not be a correction for multiplicity across the three separate cohorts.

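### Phase 1b enrolment text in 4.3 and 3.1.2.3 conflicts with the mandatory stage-1 stop in 7.1 and the synopsis; followed literally, 4.3 would give a per-cohort type I error of 0.1185

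*Combined protocol and SAP*

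**What the plan says.** Section 7.1 sets up a Simon two-stage design in each of three disease cohorts. Stage 1: "In the first stage, 13 patients of each cancer will be accrued". Futility rule: "If there are 1 or fewer responses in these 13 patients, that cohort will be stopped". Continuation: "Otherwise, 21 additional patients of the same disease cohort will be accrued for a maximum total of 34 patients per disease cohort". Final rule: "Each of the three null hypotheses will be rejected if 6 or more responses are observed in 34 patients for each cohort". The stated properties are a type I error of 0.1 and 80% power at a 25% response rate, with no multiplicity correction across cohorts. The synopsis gives the same mandatory stop. Section 7.1 also carries dose-escalation patients treated at the MTD over into the matching two-stage cohort.

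Three other sections describe Phase 1b enrolment differently:

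- **Section 4.3** caps each cohort at 34, then says "Enrollment will be open for all cohorts in parallel and will continue until the enrollment target is reached". The only event that closes a cohort is its being full, and the Phase 1b total is put at about 102. There is no mention of stage 1 and no cross-reference to 7.1.
- **Section 3.1.2.3** permits, but does not require, recruitment to be suspended or ended when the target response rate looks unlikely. It gives no number.
- **Section 3.2.1** names the two-stage design but words stage 1 as "At least 13 patients per each disease cohort" and gives 102 as the expected total.

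**The concern.** Section 4.3 is where study staff look to see who may be enrolled and when a cohort closes. Read alone, it takes an open cohort through to its target whatever stage 1 shows. Section 3.1.2.3 turns a fixed futility boundary into a judgement. Section 7.1 does neither.

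Two things depend on which text is followed. The first is the operating characteristics: the stated type I error relies on a cohort with 0 or 1 response in 13 having no further route to a positive result. The second is exposure: the two-stage design exists to limit how many patients receive an inactive three-drug regimen, and that protection is lost if the stop is not applied.

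The interim read also takes time. The first on-treatment scan is at 8 weeks (5.3.2.1.1) and 5.3.2.1 counts confirmed responses. No section says whether accrual pauses meanwhile, or what happens to patients entered before the stage-1 count is known.

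**Working it through.** **Inputs (Section 7.1).** Null rate 0.10, one-sided; alternative 0.25; n1 = 13, stop if X1 ≤ 1; n2 = 21, total 34; reject if X1 + X2 ≥ 6. X1 and X2 are independent binomial counts with common rate p.

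**Step 1: the plan's own figures, stop binding.**

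P(reject) = Σ over x = 2 to 13 of P(X1 = x) × P(X2 ≥ 6 − x).

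At p = 0.10:

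| x | P(X1 = x) | P(X2 ≥ 6 − x) | Product |
|---|---|---|---|
| 2 | 0.2448 | 0.1520 | 0.0372 |
| 3 | 0.0997 | 0.3516 | 0.0351 |
| 4 | 0.0277 | 0.6353 | 0.0176 |
| 5 | 0.0055 | 0.8906 | 0.0049 |
| ≥ 6 | 0.0009 | 1 | 0.0009 |

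The sum is 0.0957. The same formula at p = 0.25 gives 0.811. The stated 0.1 and 80% are therefore the nominal bounds that this design meets.

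**Step 2: stop not applied, 6 or more of 34 still rejects.**

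P(Bin(34, 0.10) ≥ 6) = 0.1185 and P(Bin(34, 0.25) ≥ 6) = 0.886.

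The difference in type I error comes entirely from cohorts that 7.1 would have closed:

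- X1 = 0: 0.2542 × 0.0144 = 0.0037
- X1 = 1: 0.3672 × 0.0522 = 0.0191 (unrounded inputs)

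Together 0.0228, and 0.0957 + 0.0228 = 0.1185. So the excess arises only if a cohort with 0 or 1 response in 13 may later be called positive. Enrolling more patients without that permission leaves the error at 0.0957.

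**Step 3: enrolment.**

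P(stop at stage 1) at p = 0.10 is 0.2542 + 0.3672, or 0.6213 from unrounded terms. At p = 0.25 it is 0.1267.

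Expected size per cohort = 13 + 21 × (1 − P(stop)):

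- p = 0.10: 13 + 21 × 0.3787 = 20.95, about 63 over three cohorts
- p = 0.25: 13 + 21 × 0.8733 = 31.3, about 94 over three cohorts

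Without the stop it is 34 per cohort and 102 in total at either rate.

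**Step 4: what a total of 102 implies.** 102 = 3 × 34, so it is reached only if all three cohorts pass stage 1. Assuming independent cohorts, that has probability 0.3787³ = 0.054 if all are at 10% and 0.8733³ = 0.666 if all are at 25%. It is a ceiling, not an expected total.

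**Step 5: why the wording in 3.2.1 matters.** If the same boundary of 1 or fewer were read at a larger first stage, with the total still 34 and 6 or more still rejecting, the Step 1 formula gives 0.1006 at n1 = 14 and 0.1047 at n1 = 15. The decision has to be taken on exactly 13.

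**The case against.** The strongest reply is that the stop is stated in mandatory terms twice, in the synopsis and in 7.1, and nothing in 4.3 cancels it. Section 4.3 is titled for patient identification, contains no test rule, and introduces 34 as a maximum. A cap with cohorts opened in parallel is compatible with a two-stage design. This stands, and it limits what can be claimed. Four stronger readings are tempting, and the documents do not support them:

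- **That 4.3 orders every cohort to 34.** This is inferred from the target, from cohorts closing only when full, and from the total of 102. The cap is worded as a maximum.
- **That the plan's type I error exceeds 0.10.** Under the rule in 7.1 it is 0.0957. The 0.1185 needs a positive claim from a cohort that 7.1 would have closed.
- **That parallel or uninterrupted accrual inflates the error by itself.** Step 2 shows that it does not while the decision on the first 13 binds.
- **That stage 1 has no fixed size.** The synopsis and 7.1 both fix it at 13, and 3.2.1 itself implies 34 − 21 = 13. Its opening words can be read as the minimum enrolment per cohort.

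The reply does not remove the conflict. A reader following 4.3 finds no stop, a reader following 3.1.2.3 finds an optional one, and a reader following 7.1 finds a binding one. No section says which governs.

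**Conclusion.** The concern holds as an inconsistency between enrolment rules: 4.3 and 3.1.2.3 against 7.1 and the synopsis. It should be corrected, but it is not a flaw in the two-stage design, whose stated properties reproduce.

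The statistical cost of following 4.3 literally is modest: 0.1185 against 0.0957, about 1.9 points above the stated 0.10, with power rising from 0.811 to 0.886. The larger cost is exposure: 34 − 20.95, or about 13 more patients per inactive cohort and 102 − 63 = 39 across three, at a true rate of 10% in each.

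The figures assume exact binomial counts, 13 then 21 evaluable patients, and an unchanged final boundary; totals across cohorts assume the same rate in each. The number who would enter while stage 1 is being read is not estimated, because the documents give no accrual rate.

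**What to change.** - **Section 4.3.** Say that 34 per cohort and 102 in total are maxima, reached only where at least 2 responses are seen in the first 13 response-evaluable patients of a cohort. Count dose-escalation patients carried over under 7.1 towards those 13 and towards the 34. Add that the decision uses those first 13 only, and that a cohort failing it closes and cannot be declared positive, whatever has been enrolled meanwhile. Cross-refer to 7.1.
- **Section 3.2.1.** Where it now reads "At least 13 patients per each disease cohort", give the number as 13 without the qualifier, and describe 102 as a maximum.
- **Section 3.1.2.3.** Replace the discretionary wording with the rule in 7.1. If discretion to stop for other reasons is wanted, state it as additional to that rule.

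The cost is wording in three sections. Sample size and boundaries do not change. An accrual pause in a cohort is needed only if the sponsor chooses one; the type I error does not require it.
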